10.10.6 Subject Characteristics and Disposition

The subjects' age, weight, ethnic background, and other demographic characteristics will be summarized by treatment group. All subjects who discontinue the study will be identified and reasons for their discontinuation will be recorded.

10.10.7 Assessment of Protocol Compliance

Every attempt will be made to select subjects who are eligible and will comply with the protocol. Noncompliant subjects may be discontinued from the study. Protocol deviations will be listed and summarized by treatment arm.

11 RISKS AND DISCOMFORTS TO STUDY SUBJECTS**11.1 LACTIN-V and Placebo Applicator Users****11.1.1 Risks**

The potential risks of LACTIN-V are currently unknown. Pelvic examinations and analyses of vaginal discharge and vaginal microbiota were included in the Phase 1 studies designed to assess LACTIN-V's safety and colonization. The initial Phase 1 safety study of LACTIN-V in healthy women, Protocol LV-001, included colposcopy to evaluate for inflammation or other lesions of the vaginal, cervical or vulvar epithelium. There were no significant differences noted in these safety parameters between treated subjects and those who remained untreated or received the placebo capsule (Osel, Inc., personal communication).

Risks from the administration of LACTIN-V are low since colonization with this type of organism is strongly associated with improved vaginal health. No systemic risks are anticipated, since this is an organism that is applied topically, and thus not absorbed. These risks will be explained in the written informed consent form. Pregnant women, fetuses, prisoners, children, persons with or at risk of STD or women undergoing in vitro fertilization will not be included in this study.

Potential risks to subjects participating in this study include genital or vaginal irritation or symptoms. In the initial Phase 1 study of LACTIN-V (LV-001), the following adverse events were experienced in (at least two) more LACTIN-V treated subjects when the treated groups were compared to the placebo and untreated groups: vaginal discharge, abdominal pain, genital pruritis, vaginal odor, vaginal burning sensation, vaginal candidiasis and diarrhea (Osel, Inc., personal communication). There is also the risk of an allergic reaction to the latex in the condoms provided to subjects who are unaware of their latex allergy and who use these condoms.

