6.2.1.2.2 Exclusion Criteria

1. Complicated cystitis or pyelonephritis (uncomplicated or complicated)
2. Vaginal or cervical infection, currently or within the past 30 days, with bacterial vaginosis (treated, symptomatic infection), yeast, *Trichomonas vaginalis*, *Neisseria gonorrhoeae*, *Chlamydia trachomatis* or genital Herpes simplex.

3. Symptomatic BV and/or yeast at Visit 1 (women who have Asymptomatic BV at Visit 1 may participate in the study).
4. High risk for sexually transmitted diseases and/or HIV, including: diagnosis of *N. gonorrhoeae*, *C. trachomatis* or *T. vaginalis* on two or more occasions during the previous six months;
5. History of chronic vaginal, urinary or pelvic symptoms not attributable to UTI.
6. Pregnancy or within two months of last pregnancy (all subjects must have a negative urine pregnancy test prior to randomization).
7. Lactation.
8. Antibiotic therapy (vaginal or systemic) less than three days prior to Randomization Visit (Visit 1).
9. Antifungal therapy (vaginal or systemic) less than thirty days prior to the Randomization Visit.
10. Antibiotics planned within four months (including prophylactic antibiotics).
11. Investigational drug use within 30 days or current participation in any urogenital studies.
12. Menopause.
13. Any significant disease or acute illness that in the Investigator's assessment could complicate the evaluation.
14. Known HIV infection.
15. Immunosuppressive drug within 60 days.
16. Known allergy to any component of LACTIN-V or the placebo capsule.
17. Unavailable for follow-up visits.
18. Have any social or medical condition that, in the opinion of the Investigator, would preclude provision of informed consent, make participation in the study unsafe, complicate interpretation of study outcome data, or otherwise interfere with achieving the study objectives.

Subjects who develop the following exclusion criteria while on study will discontinue study treatment, but continue to be followed for safety and efficacy endpoints whenever possible.

- Pregnancy
- Lactation
- HIV infection
- Treatment with immunosuppressive drug
- Allergy to LACTIN-V or placebo capsule

Subjects who develop any other exclusion criteria while on study will be managed at the discretion of the Investigator, in consultation with the Medical Monitor.

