6.2.1.4 Withdrawal of Randomized Subjects

Study subjects who have been randomized may be withdrawn from receiving further investigational product for the following reasons:

1. Allergy to the study product.
2. Adverse event.
3. Unable or unwilling to use LACTIN-V applicators for the duration of the study.
4. Failure to follow protocol requirements that would significantly affect study outcomes.
5. Pregnancy.
6. Medical reasons unrelated to study products. This determination will be at the discretion of the Investigator, but might include major new diagnoses such as a malignancy requiring chemotherapy.
7. Personal reasons (voluntary request or withdrawal of consent).
8. Physician decides that it is not in the best interest of the subject to continue participation.
9. Physician or sponsor decides, for whatever reason, to discontinue the study.

For randomized subjects who are withdrawn from receiving further product, the site will make every effort to continue to follow all subjects for efficacy through duration of study.

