6.2.1.5 Discontinuation and Subject Replacement

The study subject may choose to leave the study at any time. Reasons for leaving the study will be recorded. Study subjects who enroll in the study but who do not return after three attempts to contact them will be considered study “lost to follow-up”.

Once a subject is randomized, she will not be replaced. Withdrawals and drop-outs will not be replaced.

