6.5 Early Discontinuations

If a study subject should discontinue the study prior to Visit 6, all end of study procedures and CRFs should be completed.

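### Section 10.10.7 allows noncompliant women to be discontinued from the study, while 6.2.1.4 withdraws them from product only and keeps them in follow-up; reconcile the two so that UTI outcomes are not lost after randomization

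*Combined protocol and SAP*

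**What the plan says.** Section 10.10.7 (Assessment of Protocol Compliance) states: "Noncompliant subjects may be discontinued from the study". It does not define noncompliance, name a decision-maker or mention later follow-up.

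Section 6.2.1.4 (Withdrawal of Randomized Subjects) covers the same behaviour differently. Its list opens: "Study subjects who have been randomized may be withdrawn from receiving further investigational product for the following reasons". Item 4 is: "Failure to follow protocol requirements that would significantly affect study outcomes". For women withdrawn from product, "the site will make every effort to continue to follow all subjects for efficacy through duration of study".

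Three other provisions bear on the point:

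- Section 6.2.1.2.2 says that women who develop any of five listed conditions on study (pregnancy, lactation, HIV infection, immunosuppressive treatment, allergy to product) "will discontinue study treatment, but continue to be followed for safety and efficacy endpoints whenever possible". Noncompliance is not on that list.
- Section 6.5 says: "If a study subject should discontinue the study prior to Visit 6, all end of study procedures and CRFs should be completed".
- Section 6.2.1.5 says: "Withdrawals and drop-outs will not be replaced".

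Section 10.7 uses the MITT cohort (randomized, at least one dose) for the primary and secondary endpoints. Section 10.10.6 has discontinuations identified and their reasons recorded. Neither section says how an outcome missing after discontinuation is to be handled.

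**The concern.** Stopping product and leaving the study are different events. After the first, the woman's UTI outcome can still be observed; after the second it cannot. For a noncompliant woman, Section 6.2.1.4 prescribes the first and Section 10.10.7 permits the second.

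Noncompliance arises after randomization and may depend on the product. Section 2.2.2.2 reports that in LV-003 nausea, diarrhea, dysuria, vaginal discharge and vaginal odour were at least 5 percentage points more frequent on LACTIN-V. Section 11.1.1 lists discharge, itching, odor and burning among the events seen in more treated women in LV-001. Effects of this kind could reduce applicator use more in one arm even though assignment is blinded.

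If such women are removed, the MITT analysis keeps them in its definition but lacks their outcomes after exit. All three primary analyses are exposed: the proportion with any UTI (10.9.1), the number of episodes per subject (10.9.2) and time to first UTI (10.9.3).

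**Working it through.** **1. The two rules side by side.**

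| | Section 6.2.1.4, item 4 | Section 10.10.7 |
|---|---|---|
| Trigger | Failure to follow protocol requirements, with significant effect on outcomes | Noncompliance, undefined |
| What ends | Further product | Participation in the study |
| Later UTI outcomes | Every effort to collect through the study | Not addressed; 6.5 supplies one set of end-of-study procedures at exit |

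The sentence before the one at issue in 10.10.7 concerns selecting suitable women. Only an enrolled woman can be discontinued, however, so that context does not remove the conflict.

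**2. The plan's own figure.** Section 10.4 gives 250 women, 40% recurrence, a 50% reduction (40% vs 20%) and more than 80% power. Assume two-sided alpha 0.05, which Section 10.4 does not state, and 125 per arm:

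z = [0.20·√125 − 1.96·√(2·0.30·0.70)] / √(0.40·0.60 + 0.20·0.80) = (2.236 − 1.270)/0.632 = 1.527, so power = 0.937.

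This agrees with the stated bound. Random loss of 10% (112.5 per arm) leaves 0.911, and 20% (100 per arm) leaves 0.876. Power of 80% needs 82 per arm, so 1 − 82/125 = 34% could be lost at random first. Power is therefore not the main issue.

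**3. Events not seen (illustration).** Inputs: 138 per arm (276/2, Sections 4.3 and 5.1); 40% vs 20% over 16 weeks (Sections 10.4 and 10.1). Assumed: constant hazard, removal at week 6, fraction f removed. With S(t) = (1 − p)^(t/16), events lost = 138 · f · [S(6) − S(16)].

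- Placebo: S(6) = 0.6^0.375 = 0.8257 and S(16) = 0.60. At f = 10%, 13.8 × 0.2257 = 3.1 of 55.2 events.
- Active: S(6) = 0.8^0.375 = 0.9197 and S(16) = 0.80. At f = 10%, 13.8 × 0.1197 = 1.7 of 27.6 events.
- For f from 5% to 15%: 1.6 to 4.7 placebo and 0.8 to 2.5 active events.

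With equal removal the contrast hardly moves. Counting removed women in the denominator, (55.2 − 3.1)/138 = 37.8% and (27.6 − 1.7)/138 = 18.8%, a ratio of 0.50.

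**4. When the comparison is biased (no true effect, assumed removal rates).**

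- *Crude proportion, removed women counted as event-free after exit.* True risk is 30% in both arms, with 20% vs 5% removed at week 6. The observed proportion is (1 − f)·0.30 + f·[1 − 0.7^0.375], where 1 − 0.7^0.375 = 0.125. This gives 26.5% vs 29.1%, a gap of 2.6 points. The standard error is √(0.278·0.722·2/138) = 0.054, so the gap is about half a standard error.
- *Same model, Kaplan-Meier.* Removed women have the same hazard as the others, so censoring is non-informative. The estimate is 30% in both arms, and the false difference is zero.
- *Removal related to risk, removed women excluded.* True risk is 40% in both arms, and removed women have risk r. The observed risk is (0.40 − f·r)/(1 − f). With 20% active vs 5% placebo removed: r = 50% gives 0.375/0.395, RR 0.95; r = 60% gives 0.350/0.389, RR 0.90. At 125 per arm the two-sided type I error is 0.060 and 0.092. Equal removal of 10% in both arms gives RR 1.00.

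**The case against.** The strongest reply is that 10.10.7 is permissive and vague, and the rest of the protocol points the other way. Section 6.6 handles a missed applicator by skipping or late use with a diary entry, and does not mention removal. Section 10.7 lets women with significant deviations into the Eval cohort and deals with non-adherence through the ATP cohort. Blinding limits differential removal. All of this stands. It makes routine removal less likely, but it does not say which section governs, and it shows that removal serves no analytic purpose.

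Four stronger readings are tempting, and the documents do not support them.

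- *Outcomes will be lost, by staff decision.* Section 10.10.7 says only that discontinuation may happen and names no one who decides. Data up to exit are kept under 6.5.
- *The noncompliant woman faces three rules.* She faces two, because the five conditions in 6.2.1.2.2 do not include noncompliance.
- *Women who stop because of an adverse event are followed for efficacy but not for safety.* Section 6.2.1.4 is silent on safety and does not exclude it. Adverse events are queried at all visits (4.4.2), recorded at follow-up visits (6.3.5) and all to be recorded (7.1.1). Serious events are followed to resolution (7.2) and pregnancies for outcome (7.7). Allergy and pregnancy also fall under 6.2.1.2.2, where women "continue to be followed for safety and efficacy endpoints whenever possible".
- *The 2.6-point gap measures informative censoring.* It does not. It arises only in a crude proportion that counts removed women as event-free, which the plan does not prescribe. Kaplan-Meier under the same model shows no gap.

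**Conclusion.** The conflict between 10.10.7 and 6.2.1.4 is certain from the text, and nothing in the documents resolves it. If 10.10.7 is applied, primary outcomes after exit are lost in women selected by post-randomization behaviour, with no replacement and no missing-outcome rule.

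Whether that biases the result depends on facts the plan does not give. Crude proportions are affected when removal differs by arm. Time to first UTI is affected when removal is related to UTI risk, and the comparison is distorted under no true effect only if this happens differently in the two arms. The documents contain no removal rates, so the bias cannot be sized; the figures above are illustrations under assumed rates, timing and risks.

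The point merits correction because the loss is avoidable and the outcomes cannot be recovered later.

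**What to change.** 1. **Section 10.10.7.** Reconcile it with 6.2.1.4 so that noncompliance is not by itself a reason to end follow-up. State that any randomized woman who stops product continues the scheduled visits through Visit 6 unless she withdraws consent, is lost to follow-up, or the study is stopped. The last exception is needed because 6.2.1.4 (item 9) and 8.4 allow the study itself to be discontinued, suspended or terminated. This concerns data collection only; when product should be stopped remains for the sponsor to settle.
2. **Section 6.2.1.4.** As a minor alignment, extend the follow-up clause to name safety as well as efficacy, matching 6.2.1.2.2.
3. **Section 6.5.** Leave it unchanged. It preserves data at exit and is needed whenever a woman leaves, including when the study is stopped.

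The cost is a wording change in two sections, plus completing the remaining visits for women who would otherwise have been removed. Those visits are already in the schedule, but the documents give no budget, and 11.1.5 prorates payment by visit, so some expense per woman should be expected.

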11.1.2 Benefits

Research subjects, whether they receive LACTIN-V or placebo, will have the benefit of an office visit and urine culture, often omitted for this condition. Subjects will also have the benefit of having a pap smear. In addition, subjects participating in this clinical trial may contribute to the body of knowledge in the field of preventing recurrent urinary tract infections.

11.1.3 Procedures for Minimizing Potential Risks

Allergic Reactions (including anaphylaxis): A study subject with a known allergy to components of the capsule will be excluded from enrollment. If an allergy or sensitivity

occurs during the course of the study, the study subject will be advised to immediately discontinue product use and seek medical attention. This event will be recorded on an Adverse Event (AE) Form.

Allergies to Latex: Subjects with known allergy to latex will be provided with non-latex condoms.

11.1.4 Compare Potential Benefits with Potential Risks

The potential benefits to women with a history of recurrent UTI will depend on the outcome of the study. The subjects in this study will have the benefit of a pap smear, urine culture, and several pelvic examinations. These procedures may detect underlying diseases sooner.

11.1.5 Costs and Compensation

The subjects will not be charged for any of the study visits, study supplies or examinations. Subjects will be reimbursed for study participation to cover inconvenience, travel, parking and time off work. The visits will be prorated and partial payment given in the event that the subject only completes a portion of the study. The subject will be responsible for any medical care related to pregnancy that occurs during study participation. If a subject is diagnosed with a recurrence of UTI, vaginal candidiasis, BV, STD or other infection during this study, the subject will be responsible for the cost of any treatment not provided by the study site or covered by their insurance.

Dispense condoms		X					
Safety assessment			X	X	X	X	X

APPENDICES

Appendix A Nugent Scoring System for Gram Stained Vaginal Smears

Appendix B Instructions

Appendix C Diary

Appendix A

Nugent Scoring System for Gram Stained Vaginal Smears

The Nugent scoring system uses a 0- to 4-point scale for the evaluation of the vaginal microbiota and is based on the weighted sum of the following three bacterial morphotype scores calculated from slide exam under oil immersion (1000X):

- *Lactobacillus*: large Gram-positive rods
- *Gardnerella/Bacteroides* spp.: small Gram-variable *coccobacilli*/small Gram-positive rods
- *Mobiluncus* spp.: thin, curved Gram-variable rods

The criterion for bacterial vaginosis according to Nugent's criteria is a total score of 7 or more with a score of 4 to 6 being considered intermediate and a score of 0 to 3 being considered normal.

Nugent Scoring System for Gram's Stained Vaginal Smears ¹			
SCORE ²	Lactobacillus morphotypes	Gardnerella/Bacteroides spp. morphotypes	Curved Gram-variable rods
0	4+ ³	0	0
1	3+	1+	1+ or 2+
2	2+	2+	3+ or 4+
3	1+	3+	
4	0	4+	

1 Source: Draft Guidance for Industry: Bacterial Vaginosis – Developing Antimicrobial Drugs for Treatment (July 1998)

2 Morphotypes are scored as the average number seen per oil immersion field (minimum of 10–20 fields should be examined). Each morphotype is then given a score from the left hand column. The TOTAL SCORE is calculated by adding up the individual morphotype scores = *Lactobacillus* + *Gardnerella/Bacteroides* + curved Gram-negative rods.

3 QUANTIFICATION SCALE: 0 = no morphotypes seen; 1+ = < 1 morphotype per field; 2+ = 1 to 4 morphotypes; 3+ = 5 to 30 morphotypes; 4+ = > 30 morphotypes per field.

Appendix B

Study Diary Instructions

The "Diary" on the other side will help you to record when you insert your study applicators. Please mark the daily boxes to record any activity or symptoms.

When to Insert the Study Applicator

You will use the first applicator in the clinic on Day 1. All other applicators will be used at bedtime.

Starting tomorrow evening, you will insert an applicator at bedtime. Continue using one applicator a day at bedtime. For the first week, you will be inserting an applicator daily for 5 days. In the following weeks, it will be done once a week. The study staff will mark your diary for the recommended SCHEDULED DATE.

If you forget to insert the applicator please insert it as soon as you remember.

Recording When You Insert the Study Applicator: Use the Diary on the Other Side

Write the date and time in the Diary box for each applicator that you insert (Dose 1, Dose 2, etc.). If you insert your applicator after midnight, record the actual date and time of insertion.

Recording Activity

Check the box for each day on which an activity occurred.

Recording Symptoms

Write **1=Mild, 2=Moderate or 3=Severe** in the box for each symptom you have during the first 7 days of the study.

To Insert A An Applicator

Wash your hands thoroughly with warm water and soap.

Open **one** applicator package. Do not use anything sharp, like scissors, which could damage the applicator.

Holding the applicator between your thumb and fingers, insert into the opening of the vagina (like a tampon), and push plunger to dispense the contents.

Storage and General Instructions

Store the applicators in their box at room temperature until use.

Please avoid having sexual intercourse for 24 hours after use or use the condoms provided by the study.

Do not use another vaginal product, such as contraceptive creams, gels, foams, sponges, lubricants, douches, etc. during this study unless your doctor prescribes it.

Do not use tampons for 24 hours after applicator use.

Do not insert the applicator if you are having heavy bleeding from your period.

If you lose or damage an applicator, use another instead. If you somehow lose or damage more than 2 applicators or the whole box, please call the study clinic immediately for further instructions.

Place used applicators back in their original pouches and return at clinic visits, and return any unused applicators at the end of the study.

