At Visit 1, each subject who continues to meet all inclusion and exclusion criteria will be randomized and will receive a box containing 15 applicators. Two extra applicators will be kept at the study site in case a lost or damaged applicator needs to be replaced. The first study applicator will be inserted under supervision in clinic at this visit. The remaining 14 applicators will be inserted daily at bedtime on Days 2–5, and then weekly. Women are to abstain from sexual intercourse and tampon use for 24 hours after each applicator is used. If the subject's partner uses condoms, they will be instructed to use non-spermicidal condoms to avoid killing the *L. crispatus*. The use of other intravaginal products including douching is prohibited throughout the four-month study period. Subjects must agree not to self-medicate with antibiotics or antifungals during the four-month study period. However, subjects may be treated for any on-study vaginal or other infection if a health care provider deems such treatment necessary. Subjects who receive antibiotic or antifungal treatment after commencing the study should continue to insert the study applicator according to their allocated schedule.

Subjects will be provided with a Study Diary to use to record applicator use information during the study. The Study Diary will also be used by subjects to record any symptoms. Subjects will be instructed on how to use these memory aids to remind them to insert the applicator on the designated day and to record the date and time when each applicator was inserted.

Self-reported symptoms will be evaluated at all study visits. Subjects will be queried about the following symptoms:

Nausea or vomiting
Abdominal Discomfort
Diarrhea
Constipation
Rash
Abnormal Vaginal Discharge/Bleeding
Abnormal Vaginal Odor
Genital itching or burning
External genital irritation/swelling
Painful Urination
Urinary Frequency
Urinary Urgency
Blood in urine

Headache
Other: _____

Other: _____

Subjects will be instructed to call the study clinic if they have any unexpected symptoms at any time during the study.

Pelvic examinations will be performed at all visits to evaluate the external genitalia; cervix and vaginal mucosa for signs of irritation at Visits 1 and 6 and if clinically indicated.

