6.2.1.2 Eligibility

6.2.1.2.1 Inclusion Criteria

1. Pre-menopausal women aged 18–45 years of age at date of the Screening Visit.

2. Meets criteria for current symptomatic acute uncomplicated cystitis, defined as one or more UTI symptoms (dysuria, urgency, frequency, suprapubic pain), and pyuria (>10 wbc) on hemocytometer count, confirmed with a positive urine culture with greater than 10^2 /ml of an uropathogen.
3. Completion of all screening procedures. Screening will take place at the visit at which acute uncomplicated cystitis (UTI) diagnosis is made.
4. History of one Symptomatic UTI episode treated within the past 12 months.
5. Agree to return for the Randomization Visit (Visit 1) within 3–10 days of completing antibiotic treatment for UTI.
6. Regular menstrual cycles (21–35 days) or amenorrheic due to birth control method. Women using IUD(C) must be 2 months post insertion of IUD.
7. Subject is willing to insert vaginal applicators.
8. Capable of providing informed consent.
9. Able to read and understand English.
10. Agree to abstain from self-medication with antibiotics for UTI symptoms.
11. Agree to abstain from antibiotic prophylaxis for recurrent UTI.
12. Agree to abstain from the use of any other intra-vaginal product (i.e., contraceptive creams, gels, foams, sponges, lubricants, douches, etc.).
13. Agree to abstain from sexual intercourse for 24 hours after each applicator is inserted.
14. Agree to not use tampons for 24 hours after each applicator is inserted.
15. Agree to use an adequate method of birth control throughout study to avoid pregnancy. Acceptable methods include bilateral tubal-ligation, male partner with a vasectomy, steroidal contraceptive (oral, patch, injectable, implantable), IUD, condoms (to be provided), or abstinence. If condoms are used, they should be non-spermicidal condoms provided by the site.

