6.6 Missed Applicators

During the initial five-day treatment period, if it is already within eight hours of her next dose, she should skip the missed applicator. The subject should record the missed dose on the Study Diary. After Day 5, if a subject misses an applicator, she should be instructed to use the missed applicator as soon as possible (but no more than four days from the scheduled date) and the date should be recorded on the Study Diary.

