10.7 Cohorts for Analyses

The intent-to-treat (ITT) cohort is defined as subjects who are randomized in the study.

The modified intent-to-treat (MITT) cohort is defined as subjects who are randomized and have received at least one dose of study product. It is a subset of the ITT cohort. It will be used for analyses of primary and secondary endpoints, baseline characteristics, trial conduct, and significant protocol deviations.

The evaluable (Eval) cohort is defined as the subset of the MITT cohort who had at least one follow-up visit assessment post-baseline (Visit 2 or later) and are not an antibiotic treatment failure at Visit 1 (defined as a requiring treatment for UTI symptoms at Visit 1). Subjects with any significant protocol deviations may be included in this cohort.

The according-to-protocol (ATP) cohort is the subset of Eval with subjects who meet all protocol specifications. Those subjects who developed exclusion criteria while on study will be excluded from this cohort.

Both Eval and ATP cohorts will be used to analyze the primary endpoints.

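### The participant sheet (Appendix B) conflicts with the protocol on intercourse after dosing and on missed applicators, so a woman who follows it can depart from the protocol and, on a literal reading, lose her place in the ATP cohort

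*Combined protocol and SAP*

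**What the plan says.** **Intercourse after an applicator.** Section 5.1 sets the conduct rule: "Women are to abstain from sexual intercourse and tampon use for 24 hours after each applicator is used". Inclusion criterion 13 makes it a condition of entry: "Agree to abstain from sexual intercourse for 24 hours after each applicator is inserted". Appendix B tells the participant: "Please avoid having sexual intercourse for 24 hours after use or use the condoms provided by the study".

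**Forgotten applicators.** Section 6.6 has two rules. For the daily phase: "During the initial five-day treatment period, if it is already within eight hours of her next dose, she should skip the missed applicator". After Day 5 the missed applicator is to be used promptly, but "no more than four days from the scheduled date". Appendix B has one sentence for all doses: "If you forget to insert the applicator please insert it as soon as you remember".

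**Who receives what.** Section 6.4.2 supplies Appendix B to each subject as written instructions. It also says that she will be told what to do about a forgotten applicator, and cross-refers to Section 6.6.

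**Cohorts.** Section 10.7 defines ATP as the "subset of Eval with subjects who meet all protocol specifications" and also excludes women who develop exclusion criteria on study. Primary endpoints are to be analysed in MITT, Eval and ATP. MITT needs one dose only, and Eval may include women with significant deviations.

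**The concern.** Participants will act on the sheet they take home. If it permits conduct that the protocol body does not, a woman can do as she was told in writing and still be recorded as departing from the protocol. Section 8.6 lists departures in product administration among possible significant deviations, and Section 10.10.7 has deviations summarised by arm.

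The statistical stake is the ATP cohort. Its definition demands that every specification be met, without listing which departures exclude. With two conflicting rules in force, membership depends on which text the person classifying the subject has in hand, and that classification concerns behaviour after randomisation. Post-randomisation selection in a cohort used for the primary endpoints is the main worry, more than loss of numbers.

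**Working it through.** The point is textual, so the check sets the current passages side by side and asks when they disagree, whether anything reconciles them, and what follows for the cohorts.

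**1. Where the rules disagree**

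| Situation | Protocol body | Appendix B | Conflict |
|---|---|---|---|
| Daily phase, remembered more than 8 h before the next dose | Skip rule does not apply (6.6) | Insert | No |
| Daily phase, remembered within 8 h of the next dose | Skip (6.6) | Insert | Yes |
| Weekly phase, remembered up to 4 days late | Use promptly (6.6) | Insert | No |
| Weekly phase, remembered more than 4 days late | Outside the limit (6.6) | Insert | Yes |
| Intercourse with a study condom within 24 h of an applicator | Not permitted (5.1; agreed to under criterion 13) | Offered as an alternative | Yes |
| Tampon within 24 h of an applicator | Not permitted (5.1, criterion 14) | Not permitted | No |

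On nominal intervals of 24 hours and 7 days, the missed-dose texts agree for the first 24 − 8 = 16 hours and the first 4 days. They disagree for the last 8 hours and the last 7 − 4 = 3 days. Followed literally, the sheet permits two daily-phase insertions less than eight hours apart.

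**2. Does anything reconcile them?**

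- Missed applicators: in part. Counselling under 6.4.2 refers to 6.6, so a participant may hear the limits, but her written sheet omits them.
- Intercourse: no. The condom sentence in Section 5.1 concerns condom type (non-spermicidal) and does not relax abstinence. Criterion 15 lists condoms as contraception. The flow chart has condoms dispensed at Visit 1, so the alternative on the sheet is usable.
- Appendix C, the diary, is not reproduced, so what else participants take home cannot be checked.

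**3. Would the departures be visible?** Late insertions would be: Appendix B has the date and time of each one recorded. It also has activities ticked by day, but without Appendix C one cannot say whether intercourse is among them.

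**4. Cohort consequence**

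- MITT: retained, since one dose is enough.
- Eval: retained, since deviations do not exclude.
- ATP: excluded if the requirement to meet all specifications is read literally. Section 10.7 does not say whether it is to be read that way for these departures.

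**5. Size.** The documents give no rate of late doses or of intercourse after dosing, so the number affected cannot be computed. A rough bound shows whether loss of power is the issue. Inputs from Section 10.4: recurrence of 40%, halved to 20%, N = 250. Sections 4.3 and 5.1 give N = 276. No alpha is stated; two-sided 0.05 is assumed, with a pooled-variance normal approximation and no continuity correction. With p̄ = 0.30 and n per arm:

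power = Φ{[0.20·√n − 1.960·√(2·0.30·0.70)] / √(0.40·0.60 + 0.20·0.80)}

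- n = 125: Φ{(2.236 − 1.270)/0.632} = Φ(1.53) = 93.7%, consistent with the plan's claim of more than 80%.
- 80% power needs 82 per arm, or 164 women.
- ATP would fall below 80% power only if exclusions for all causes passed 1 − 164/250 = 34%, or 1 − 164/276 = 41%.

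The point does not rest on this bound.

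**The case against.** The missed-applicator half can be called an omission from a short sheet. The section that hands out Appendix B promises instruction under 6.6 and a review at each follow-up visit, and after Day 5 Section 6.6 itself asks for prompt use, so the two texts differ only beyond four days. Both arms receive the same sheet under blinding, and no between-arm difference is shown. MITT and Eval keep the women concerned. Criterion 13 is an agreement at entry, which a woman can meet and later depart from. Section 8.6 says only that significant deviations may include departures in product administration, and Section 10.7 does not name these departures as grounds for exclusion from ATP.

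Most of this stands and limits the point. The breach is conditional, the counselling is a real but partial mitigation, and the analysis effect is confined to ATP. It does not remove the conflict: counselling that differs from the written sheet leaves the participant with two rules, and the intercourse conflict has no mitigation anywhere. Criterion 13 being an agreement does not help either, because Section 5.1 states the rule directly.

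**Conclusion.** The point holds in a limited form. Appendix B contradicts Section 5.1 and inclusion criterion 13 on intercourse, and omits both limits of Section 6.6 on missed applicators. A woman following the sheet can depart from the protocol in the three situations marked as conflicts above, and a literal reading of Section 10.7 could then cost her ATP membership. How many women this would affect is unknown. It is a minor defect, but verifiable and cheap to cure.

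Three stronger inferences are tempting and are not supported:

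- That any woman who follows the sheet breaches the protocol. Outside the three situations, following it is consistent with the protocol.
- That the primary comparison as a whole is compromised. Two of the three cohorts assigned to the primary endpoints are unaffected in membership, and no imbalance between arms is shown.
- That the abstinence rule exists to protect dosing, so that condom use would undermine exposure. The documents give no reason for the rule; the only reason in Section 5.1 concerns spermicide on condoms.

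The ATP consequence assumes that its definition is applied as written. No view is taken here on which missed-applicator or intercourse rule is right.

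**What to change.** 1. Reconcile Appendix B with Sections 5.1 and 6.6 and inclusion criterion 13, so that all carry the same missed-applicator and intercourse rules. The sponsor decides which version governs.
2. Before unblinding, align the ATP definition in Section 10.7 with the reconciled rules and list the departures that exclude a subject. Say there how women who followed an already issued sheet are handled. This should follow step 1: declaring in advance that following the sheet is never a deviation would make the sheet govern ATP before the sponsor has decided.

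The cost is one reprinted participant sheet, a short protocol edit (with the approval that Section 8.1 requires) and an IRB submission. Sample size, visits and the MITT and Eval definitions do not change.
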